### **5 STUDY POPULATION**

Prospective approval of protocol deviations to recruitment and enrollment criteria, also known as protocol waivers or exemptions, is not permitted.

#### **5.1 Inclusion criteria**

Participants are eligible to be included in the study only if all of the following criteria apply:

##### **Age**

1. Study participant must be  $\geq$ 18 to  $\leq$ 89 years of age, at the time of signing the informed consent.

##### **Type of participant and disease characteristics**

2. Study participant must be seropositive for LGI1 antibody measured by LGI1 serum autoantibody cell-binding assay.

3a. Study participant must have  $\geq$ 2 seizures/week during the Screening Period or have experienced such seizures that stopped following high dose corticosteroids (500 to 1000mg MP equivalent/day):

- Either FBDS with or without other focal (partial) seizures including focal to bilateral tonic clonic
- Or focal (partial) seizures including focal to bilateral tonic clonic and fulfil the following new-onset AIE criteria:
  - a. Subacute onset (rapid progression of less than 3 months) of working memory deficits (short-term memory loss), altered mental status (defined as decreased or altered level of consciousness, lethargy, or personality change), or psychiatric symptoms.

AND

b. At least one of the following:

- i. New focal CNS finding, as per the investigator's assessment
- ii. Seizures not explained by a previously known seizure disorder
- iii. CSF pleocytosis (white blood cell count of  $>5$  cells/mm $^3$ )
- iv. MRI features suggestive of encephalitis (Brain MRI hyperintense signal on T2-weighted fluid-attenuated inversion recovery sequences highly restricted to one or both medial temporal lobes [limbic encephalitis], or in multifocal areas involving grey matter, white matter, or both compatible with demyelination or inflammation).

AND

c. Reasonable exclusion of alternative causes

4a. Study participant has initiated or re-initiated corticosteroids at a dose of 500 to 1000mg MP equivalent/day within 42 days prior to randomization. Participants re-initiating corticosteroids are eligible only if re-initiation is due to seizure rebound and within the timeframe outlined in Section 4.1.

If the study participant has initiated a steroid taper, the study participant cannot receive an oral steroid dose lower than 40mg/day when randomized.

5. Study participant with onset of disease symptom between 0 to 12 months prior to Screening, per investigator's assessment.

### **Weight**

6. Study participant weighs at least 35kg (for males and females) at Screening.

### **Sex**

7a. Male or Female

- A female participant is eligible to participate if she is not pregnant (see Appendix 4 [(Section 10.4)]), not breastfeeding, and at least one of the following conditions applies:
  - Not a woman of childbearing potential (WOCBP) as defined in Appendix 4 (Section 10.4)
  - OR
  - A WOCBP who agrees to follow the contraceptive guidance in Appendix 4 (Section 10.4) during the treatment period and for at least 90 days after the final dose of study treatment.

### **Informed consent**

8a. Study participant is capable of giving signed informed consent or has a legal representative to consent for him/her as described in Appendix 1 (Section 10.1.3) which includes compliance with the requirements and restrictions listed in the informed consent form (ICF) and in this protocol.

### **Other**

9a. Study participant has a reliable caregiver who will be available during the whole study period, as determined by the investigator.

10a. Removed in Protocol Amendment 4.

## 5.2 Exclusion criteria

Participants are excluded from the study if any of the following criteria apply:

### Medical conditions

1. Study participant has any medical or psychiatric condition that, in the opinion of the investigator, could jeopardize or would compromise the study participant's ability to participate in this study.
2. Study participant has a history of alcohol use disorder or other substance use disorder (as per Diagnostic and Statistical Manual of Mental Disorders-5) within the previous 12 months.
3. Study participant has a known hypersensitivity to any components of the study medication or any other anti-FcRn medications. This includes a known history of [REDACTED], since [REDACTED] is a constituent of the rozanolixizumab formulation.
- 4a. Study participant has a confirmed prior diagnosis of epilepsy or new onset seizures that are unrelated to LGI1 AIE or has any known or suspected medical cause for the onset of seizures other than possible AIE.
5. Study participant has a known active neoplastic disease or history of neoplastic disease within 5 years of study entry (except for basal or squamous cell carcinoma of the skin or carcinoma in situ of the uterine cervix which has been definitively treated with standard of care approaches).
6. Study participant has 12-lead ECG with findings considered clinically significant by the investigator.
- 7a. Study participant has renal impairment, defined as glomerular filtration rate (GFR) <30mL/min/1.73m^2 at the Screening Visit.
- 8b. Study participant has a clinically important active infection (including unresolved or not adequately treated infection) as assessed by investigator, including participants with a serious infection within 6 weeks prior to the first dose of IMP.
- 9a. Study participant has a history of chronic ongoing infections (eg, Hepatitis B or C, human immune deficiency virus [HIV], active tuberculosis [TB]) or who tests positive for HIV, Hepatitis B or C at the Screening Visit.
  - Presence of Hepatitis B surface antigen at the Screening Visit.
  - Positive Hepatitis C antibody test result at Screening or within 3 months prior to the IMP dose. NOTE: Study participant with a positive Hepatitis C antibody due to prior resolved disease can be enrolled only if a confirmatory negative Hepatitis C RNA test is obtained.
10. Study participant has current unstable liver or biliary disease, per investigator assessment, defined by the presence of ascites, encephalopathy, coagulopathy, hypoalbuminemia, esophageal or gastric varices, persistent jaundice, or cirrhosis. Note: An exception is stable chronic hepatobiliary conditions (including Gilbert's syndrome, asymptomatic gallstones).

11. Study participant has positive TB test at the Screening Visit unless it is determined by a TB specialist that the positive result is related to an adequately treated latent TB infection (see Section 10.12).

12. Study participants met any of the following TB exclusion criteria:

- Known active TB disease
- History of active TB involving any organ system unless adequately treated according to World Health Organization (WHO)/US Center for Disease Control therapeutic guidance and proven to be fully recovered upon consult with a TB specialist
- Latent tuberculosis infection (LTBI) (unless appropriate prophylaxis is initiated at least 4 weeks prior to IMP dosing and will be continued to completion of prophylaxis). Prophylaxis should be in accordance with applicable clinical guidelines and TB specialist judgment based on the origin of infection.
- High risk of exposure to TB infection, as assessed by the investigator
- Current nontuberculous mycobacterial (NTM) infection or history of NTM infection unless proven to be fully recovered.

For further information relating to definitions of known active TB, past history of TB, LTBI, high risk of acquiring TB infection see Section 10.12.

13. Study participant has a lifetime history of suicide attempt (including an [REDACTED] [REDACTED]), or had suicidal ideation with at least some intent to act in the past 6 months as indicated by a positive response (Yes) to either Question 4 or Question 5 of the Columbia Suicide Severity Rating Scale (C-SSRS) at Visit 1.

14. Removed in Protocol Amendment 4.

15. Study participant has a current or medical history of [REDACTED] deficiency.

16. Study participant has a history of solid organ transplant or hematopoietic stem cell transplant.

17. Study participant has undergone a splenectomy.

18. Study participant has a current or medical history of primary immune deficiency.

#### **Prior/concomitant therapy**

19. Study participant has been treated with prohibited immunosuppressants, biologics, and other therapies within the timeframe specified in Section 6.5.2.

20a. Study participant has received a live vaccination within 4 weeks prior to the Baseline Visit; or intends to have a live vaccination during the course of the study or within 8 weeks following the final dose of IMP.

#### **Prior/concurrent clinical study experience**

21. Study participant has been previously randomized in this study (rescreening for screen-failed participants is allowed with prior consultation and permission of the medical monitor/study physician).

22. Study participant has previously received rozanolixizumab drug product.

23. Study participant has participated in another study of an IMP (and/or an investigational device) within the previous 3 months or 5 half-lives prior to Baseline (whichever is longer) or is currently participating in another study of an IMP (and/or an investigational device).

### **Diagnostic assessments**

24b Alanine transaminase (ALT), aspartate aminotransferase (AST), or alkaline phosphatase (ALP) are  $>3$ x upper limit of normal (ULN).

- If study participant has  $>$ ULN for ALT, AST, or ALP that does not meet the exclusion limit at Screening, the tests must be repeated prior to dosing to ensure there was no further ongoing clinically relevant increase. In case of a clinically relevant increase as per the investigator's judgement, the study participant must be excluded.
- Tests that result in ALT, AST, or ALP up to 25% above the exclusion limit ( $>2$ xULN) may be repeated once for confirmation. This includes rescreening. If any of the repeated tests (ALT, AST, or ALP) are  $>2$ xULN, the study participant will meet the exclusion criterion #24b and the study participant must be excluded.
- For randomized study participants with a Baseline result  $>$ ULN for ALT, AST, ALP, or total bilirubin but  $<1.5$ xULN, a Baseline diagnosis and/or the cause of any clinically meaningful elevation will have to be understood and recorded in the electronic case report form (eCRF).

25. Bilirubin  $>1.5$ xULN (isolated bilirubin  $>1.5$ xULN is acceptable if bilirubin is fractionated and direct bilirubin  $<35\%$ ).

26. Removed in Protocol Amendment 5 as already incorporated in exclusion criterion #10.

27. Removed in Protocol Amendment 2, and incorporated in exclusion criterion #24.

28. Removed in Protocol Amendment 2, and incorporated in exclusion criterion #24.

29. Removed in Protocol Amendment 2, and incorporated in exclusion criterion #24.

30a. Study participant has a total IgG level  $\leq 5.5$ g/L at the Screening Visit.

31. Study participant has absolute neutrophil count  $<1500$  cells/mm^3 at the Screening Visit.

32. Study participant has a planned major elective surgical procedure for the duration of their participation in the study.

33. Removed in Protocol Amendment 4.

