## **5.4 Screen failures**

Screen failures are defined as participants who consent to participate in the clinical study but are not subsequently randomized to study treatment. A minimal set of screen failure information is required to ensure transparent reporting of screen failure participants to meet the Consolidated Standards of Reporting Trials publishing requirements and to respond to queries from regulatory authorities. Minimal information includes demography, screen failure details, eligibility criteria, and any serious adverse event (SAE).

Individuals who do not meet the criteria for participation in this study (screen failure) may be rescreened, following discussion with the sponsor's medical monitor or study physician. Rescreened participants should be assigned a new participant number for rescreening and repeat all Visit 1 assessments.

If a study participant has 1 isolated test result outside the specific range which is deemed clinically nonsignificant, the abnormal value may be rechecked at the discretion of the investigator, following discussion with the sponsor's medical monitor or study physician. If the normalization of the test result occurs within the Screening Period, then no other Screening procedures need to be repeated and the study participant may be randomized, provided all other eligibility criteria are met.

Tests that result in ALT, AST, or ALP up to 25% above the exclusion limit at Screening may be repeated once for confirmation. Eligibility assessment will be based on the best of the 2 results available before initiating randomized treatment.

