5.1 Inclusion criteria	Inclusion criterion #9 (now #9a) updated to remove requirement for caregiver to provide consent, and Inclusion criterion #10a has been removed.	To improve clarity and remove redundancy across Inclusion criteria #8a and #9a.
5.2 Exclusion criteria	Exclusion criterion #14 relating to active GI disorders has been removed.	Update in line with accumulated safety data on rozanolixizumab
5.2 Exclusion criteria	Exclusion criterion #24a amended (now #24b) to exclude when ALT, AST or ALP are >3xULN (rather than >2xULN)	Update in line with accumulated safety data on rozanolixizumab
5.2 Exclusion criteria	Exclusion criterion #33 (related to prolonged QT interval) has been removed.	This criterion is redundant as abnormalities in QT interval would be excluded by criterion #6 (clinically significant ECG findings).

Section # and Name	Description of Change	Brief Rationale
5.4 Screen failures	Text added to the third and fourth paragraphs to clarify randomization procedures after rescreening.	Clarification
6.1 Study treatments 6.3.1.1 Maintenance of study treatment blind	The dose formulation of rozanolixizumab has been updated from 'liquid in vial' to 'solution for injection'. The description of the amount of extractable volume has been removed from the description of rozanolixizumab.	To give flexibility in the supply of saline, and flexibility to use alternative vial fill volumes of rozanolixizumab.
7.1.5 Temporary discontinuation of IMP	Update of the temporary discontinuation in relation to COVID-19	Update to adapt the withdrawal criteria to the evolution of the medical practices and local guidelines with regards to COVID management
8 Study assessments and procedures	Removal of text "Protocol waivers or exemptions are not allowed."	Text is already included in Section 5 (Study population)
8 Study assessments and procedures	Text clarified to note that any additional blood samples may increase the total volume of blood collected.	Clarification.
8.2.3 Vital signs	Removed description of the time points for vital sign assessments.	To remove redundancy with the Schedule of Activities (Section 1.3).

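### Exclusion #24b states two limits for ALT, AST and ALP (>3xULN in the stem, >2xULN in the second sub-bullet), so results between them are classified both ways

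*Protocol*

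**What the plan says.** Two places in the Protocol govern eligibility on liver enzymes.

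**Section 5.2, exclusion #24b.**
- The stem begins "Alanine transaminase (ALT), aspartate aminotransferase (AST), or alkaline phosphatase (ALP) are" and sets the limit at more than 3xULN.
- The first sub-bullet covers results above ULN "that does not meet the exclusion limit at Screening, the tests must be repeated prior to dosing". The participant is excluded if the investigator sees a clinically relevant increase. It gives no multiple for the limit.
- The second sub-bullet allows one confirmatory repeat for "Tests that result in ALT, AST, or ALP up to 25% above the exclusion limit", and its parenthesis gives that limit as >2xULN. It then states the consequence when any repeat of the three tests is ">2$ xULN, the study participant will meet the exclusion criterion #24b and the study participant must be excluded".
- The third sub-bullet concerns Baseline values above ULN but below 1.5xULN in randomized participants. It sets no exclusion limit.

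**Section 5.4, Screen failures.** It restates the allowance, "Tests that result in ALT, AST, or ALP up to 25% above the exclusion limit at Screening may be repeated once for confirmation", with no multiple of ULN. It adds: "Eligibility assessment will be based on the best of the 2 results available before initiating randomized treatment".

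On the reporting side, SAP Section 5.2 provides a listing of participants who did not meet eligibility criteria, and SAP Section 6.1.2 a listing of important protocol deviations.

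**The concern.** One numbered criterion carries two thresholds for the same three analytes. The 2x figure cannot be read as a deliberately stricter bar for retests only: the parenthesis presents it as the exclusion limit itself, and the consequence cites #24b by number.

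This is a safety eligibility threshold, and Protocol Section 5 does not permit waivers, so no discretion bridges the gap. Two sites with the same laboratory results could reach opposite decisions, each with support in the text. When the data are reported, the current wording cannot settle whether a participant screened between the two figures breached #24b.

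**Working it through.** No sample size, power or alpha figure is involved. The check applies the rules as written to pairs of results (first, repeat), all in multiples of ULN.

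**Inputs.** Limit L = 3 (stem of #24b) or L = 2 (second sub-bullet). Retest band: up to 25% above the limit (#24b and Section 5.4). Decision after a retest: exclude if the repeat exceeds the limit (#24b), or decide on the better of the two results (Section 5.4).

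**Top of the retest band** = 1.25 x L: 1.25 x 3 = 3.75, or 1.25 x 2 = 2.5.

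**Worked pairs, one analyte.** Where a result is above ULN but within the limit, the investigator is assumed to see no clinically relevant increase.

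| First, repeat | Limit read as 3x | Limit read as 2x |
|---|---|---|
| 1.8, 1.8 | eligible | eligible |
| 2.4, 1.9 | eligible | eligible (2.4 is within 2.5; repeat not above 2) |
| 2.4, 2.2 | eligible | excluded (repeat above 2) |
| 2.8, 2.6 | eligible | excluded (2.8 is beyond 2.5, so no retest is offered; the repeat is also above 2) |
| 3.3, 2.9 | eligible (within 3.75; best is 2.9, not above 3) | excluded (beyond 2.5; the repeat is also above 2) |
| 3.3, 3.1 | excluded | excluded |
| 4.0, 2.5 | excluded (beyond 3.75) | excluded |

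The reading changes the answer when the deciding result is above 2x and up to 3x. Pairs wholly at or below 2x, or wholly above 3x, are unaffected. The different band ends add one further case. With 3.3 then 1.9, a 3x limit allows the retest and the participant is eligible. A 2x limit offers no retest, so 3.3 stands and excludes.

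**Is best-of-two a separate conflict?** Take one analyte and one common limit L. A retested first result is above L by definition, so the smaller of the two results exceeds L exactly when the repeat does. On a grid from 0.50 to 5.00 in steps of 0.01 (451 repeat values), the two rules disagree in:
- L = 2: 0 of 50 x 451 = 22,550 pairs
- L = 3: 0 of 75 x 451 = 33,825 pairs

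Now let Section 5.4 use 3x while the repeat rule uses 2x. For first results above 3 and up to 3.75, the two disagree exactly when the repeat is from 2.01 to 3.00: 75 x 100 = 7,500 of the 33,825 pairs. These are counts of grid points, not probabilities for patients. The mismatch of the two figures, not the best-of-two rule, produces the conflict.

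**Several analytes.** Here the wording of the two decision rules can differ even with one limit. At 3x, take ALT 3.3 then 2.8 and AST 2.9 then 3.1. Best-of-two gives ALT 2.8 and AST 2.9, so eligible. A rule that excludes if any repeat is above the limit catches AST at 3.1, so excluded.

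**The case against.** The strongest reply is that this is one mismatched figure with little left to affect. SAP Section 3 reports recruitment suspended as of 29 November 2023 with 12 participants. SAP Section 5 says all were randomized under versions up to Protocol Amendment 5, so no further eligibility decision is in view. SAP Sections 2 and 5.3.2 drop hypothesis testing, and the Randomized Set keeps everyone randomized. The criteria for important deviations sit in a separate document (SAP Section 5.1.1.2) that is not available here. Exclusion #10 and the on-study liver rules give other protection. All of this stands and limits the consequence. It does not remove the contradiction, which lies in the current text of a single criterion.

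Four stronger readings are tempting and are not supported:
- A reader might infer that Section 5.4 is a third incompatible rule. It states no multiple, and for one analyte it agrees with the repeat rule once a single limit applies.
- A reader might infer that a lone 2.4x is both eligible and excluded. At a 2x limit it lies inside the retest band, so exclusion depends on the repeat. At a 3x limit it still needs a repeat before dosing.
- A reader might infer from the Amendment 4 summary, which describes the change as "to exclude when ALT, AST or ALP are >3xULN (rather than >2xULN", that the 2x figure is a leftover and the stem is correct. The summary describes superseded text and does not say what was intended for the retest rule. The point does not rest on it, and it does not settle which limit applies.
- A reader might infer that ineligible participants were enrolled. The documents give no screening values, so this cannot be known.

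**Conclusion.** The contradiction holds: #24b gives limits of >3xULN and >2xULN for ALT, AST and ALP. It affects participants whose deciding result is above 2x and up to 3xULN, and it leaves the retest band ending at either 2.5x or 3.75xULN. Section 5.4 inherits the ambiguity because it names no figure; on its own it needs aligning only where several analytes are retested.

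The remaining effect is mainly on the eligibility and important-deviation listings for the 12 participants. No sample size, power or efficacy estimate is affected.

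One assumption matters for those listings. Only the current protocol text is available. The Amendment 5 and 6 change summaries list no change to #24b, so the same wording probably stood in Amendments 4 and 5, but those versions should be checked directly.

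**What to change.** - **Protocol:** reconcile the stem of #24b, its second sub-bullet and Section 5.4 so that one limit, one retest band and one decision rule appear throughout. The rule should say how several retested analytes are handled. Which limit applies is for the sponsor to decide.
- **SAP Sections 5.2 and 6.1.2:** assess each participant against the limit in the protocol version in force at that participant's enrolment, and state that limit in the listing. One limit applied to all 12 could mislabel participants, because they entered under different versions. Where the version in force itself carried both figures, say so and record how the case was classified. Settle this before unblinding, when SAP Section 5.1.1.2 requires important deviations to be documented.

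The cost is a protocol clarification and a short addition to two listings. No new data are needed.

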### **5.3 Lifestyle restrictions**

There are no lifestyle restrictions during the study. The use of medicinal cannabinoids and medicinal marijuana (prescribed by a physician) is permitted. The study participant must be on a stable dose of cannabinoids and/or medicinal marijuana for 4 weeks prior to Screening Visit and remain stable for the duration of the study.

#### **5.3.1 Meals and dietary restrictions**

There are no meal or dietary restrictions during the study.

### **5.3.2 Caffeine, alcohol, and tobacco**

There are no restrictions for caffeine or tobacco during the study.

Study participants are to avoid excessive alcohol consumption during the study particularly prior to the assessment of cognitive function.

